6.5.4.5 Immune cell-associated neurotoxicity syndrome (ICANS)

Immune cell-associated neurotoxicity syndrome is a neuropsychiatric syndrome which is frequently associated with CRS; however, it is specifically excluded from the definition of CRS and can occur during the course of CRS, after its resolution, or independently from CRS. Clinical findings can be progressive and may include aphasia, altered level of consciousness, impairment of cognitive skills, motor weakness, seizure, and cerebral edema. Severity is evaluated using the ASTCT Consensus grading scale, with ICE score for encephalopathy assessment (Section 10.11 of the master protocol). Recommendations for ICANS management mainly include the use of steroids, whereas tocilizumab should only be used in the context of CRS, as outlined in [Table 7](#). The proposed management should be considered only as recommendations and in light of recommendations from site specialist.

Table 7 - Guidelines for the management of immune cell-associated neurotoxicity syndrome (ICANS)

Event severity (ASTCT Consensus Grading criteria)	Recommended SAR444245 dose modification and supportive care guidelines
Mild	No intervention required other than close clinical monitoring.
Grade 1	
ICE score 7-9. Awakens spontaneously	
Moderate	SAR444245 ^a should be delayed.
Grade 2	Treatment with IV corticosteroids should be initiated as needed.
ICE score 3-6. Awakens to voice.	SAR444245 may be resumed only after participant recovery or improvement to Grade 1 after corticosteroid taper. Consideration for reduction of SAR444245 dose to █ µg/kg as per Investigator with Sponsor consultation.
Severe or Life-threatening	If Grade 3 ICANS, SAR444245 should be delayed.
Grade 3	When symptoms have resolved or improved to Grade 1 after corticosteroid taper, SAR444245 can be either restarted at █ µg/kg or permanently discontinued, as clinically indicated, and upon discussions between the Investigator and Sponsor.
ICE score 0-2. Awakens only to tactile stimulus.	
Any clinical seizure focal or generalized that resolves rapidly or nonconvulsive seizures on	

Event severity (ASTCT Consensus Grading criteria)	Recommended SAR444245 dose modification and supportive care guidelines
EEG that resolve with intervention.	If Grade 4 ICANS, SAR444245 should be permanently discontinued.
Grade 4	Treatment with IV corticosteroids should be initiated. Concomitant CRS may require tocilizumab and should be handled as described in Table 5 in Section 6.5.4.3 . Corticosteroids can then be administered IV or orally every 8 hours for up to 3 days, then tapered over 4 days.
ICE score: 0 (participant isunarousable and unable to perform ICE).	For both Grade 3 and Grade 4 ICANS
Participant isunarousable or requires vigorous or repetitive tactile stimuli to arouse. Stupor or coma.	If there is no clinical improvement within 24 to 72 hours, then re-evaluation for other contributing conditions should be done. Administration of IV Tocilizumab at 8 mg/kg (for participants weighing ≥ 30 kg, total dose should not exceed 800 mg) should be considered, and steroids should be administered concurrently and repeated as previously mentioned for CRS.
Life-threatening prolonged seizure (>5 min): or Repetitive clinical or electrical seizures without return to baseline in between.	Neurologist and other relevant clinical specialists should be involved whenever indicated.
Deep focal motor weakness such as hemiparesis or paraparesis.	
Diffuse cerebral edema on neuroimaging; decerebrate or decorticate posturing; or cranial nerve VI palsy; or papilledema; or Cushing's triad.	

a Information for preparation and storage of SAR444245 is provided in the pharmacy manual

Abbreviations: ASTCT=American Society for Transplantation and Cellular Therapy; CRS= cytokine release syndrome; ICANS= Immune effector cell associated neurotoxicity syndrome; ICE= Immune Effector Cell-Associated Encephalopathy; IV = Intravenous.

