Grade 4 ICE score: 0 (participant is unarousable and unable to perform ICE). Participant is unarousable or requires vigorous or repetitive tactile stimuli to arouse. Stupor or coma. Life-threatening prolonged seizure (>5 min): or Repetitive clinical or electrical seizures without return to baseline in between. Deep focal motor weakness such as hemiparesis or paraparesis. Diffuse cerebral edema on neuroimaging; decerebrate or decorticate posturing; or cranial nerve VI palsy; or papilledema; or Cushing's triad.	If Grade 4 ICANS, both SAR444245 and pembrolizumab should be permanently discontinued. Treatment with IV corticosteroids should be initiated. Concomitant CRS may require tocilizumab and should be handled as described in Table 8 in Section 6.5.4.3 . Corticosteroids can then be administered IV or orally every 8 hours for up to 3 days, then tapered over 4 days. For both Grade 3 and Grade 4 ICANS If there is no clinical improvement within 24 to 72 hours, then re-evaluation for other contributing conditions should be done. Administration of IV Tocilizumab at 8 mg/kg (for participants weighing ≥30 kg, total dose should not exceed 800 mg) should be considered, and steroids should be administered concurrently and repeated as previously mentioned for CRS. Neurologist and other relevant clinical specialists should be involved whenever indicated.

^a Information for preparation and storage of SAR444245 is provided in the pharmacy manual

Abbreviations: ASTCT=American Society for Transplantation and Cellular Therapy; CRS= cytokine release syndrome; ICANS= Immune effector cell associated neurotoxicity syndrome; ICE= Immune Effector Cell-Associated Encephalopathy; IV = Intravenous.

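### The ICANS text and its table disagree on tocilizumab in all three substudies, and the Grade 4 ICANS discontinuation wording differs between substudies and does not fit Cohort D2

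*Protocol*

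**What the plan says.** Section 6.5.4.5 appears in Substudies 02, 03 and 04 with nearly the same narrative. It describes ICANS as often associated with CRS but adds that "it is specifically excluded from the definition of CRS and can occur during the course of CRS, after its resolution, or independently from CRS". It then restricts tocilizumab: "tocilizumab should only be used in the context of CRS, as outlined in" the ICANS table (Table 7 in Substudies 02 and 03, Table 10 in Substudy 04).

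In the Grade 3 and 4 rows, Table 7 first deals with CRS: "Concomitant CRS may require tocilizumab and should be handled as described in Table 5". Table 10 has the same sentence, pointing to its own CRS table (Table 8). A new block follows, headed "For both Grade 3 and Grade 4 ICANS". It opens "If there is no clinical improvement within 24 to 72 hours, then re-evaluation for other contributing conditions should be done", and the next sentence, beginning "Administration of IV Tocilizumab at 8 mg/kg", says this should be considered, with steroids given concurrently.

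On stopping treatment, Table 7 in Substudies 02 and 03 reads "If Grade 4 ICANS, SAR444245 should be permanently discontinued". Table 10 in Substudy 04 says instead that "both SAR444245 and pembrolizumab should be permanently discontinued". Section 6.5.1 of each substudy allows the other study drug to continue when one component is permanently stopped.

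**The concern.** The narrative cites the table as the place where the CRS restriction is set out, and the table does not contain that restriction. For a participant with Grade 3 or 4 ICANS and no CRS, a site working from the narrative and a site working from the table would reach different conclusions about tocilizumab.

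The Grade 4 wording raises a second question. SAR444245 with pembrolizumab has the same listed dose levels in Cohorts B1 to B3, C and D1 (Table 2 in Substudies 02 and 03, Table 3 in Substudy 04). Yet pembrolizumab is expressly stopped after Grade 4 ICANS only in Substudy 04. The amendment summaries shown for Substudy 04 list no ICANS change and give no reason for the difference. At stake is consistent handling of a serious event across sites that may be running more than one substudy.

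**Working it through.** No figure in the plan depends on this point, so there is nothing to reproduce. The check is a side-by-side reading.

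**1. Tocilizumab: where narrative and table diverge (same result in all three substudies)**

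- Grade 3 or 4 ICANS with CRS: the narrative permits tocilizumab, and the table sends the CRS to the CRS table. No conflict.
- Grade 3 or 4 ICANS without CRS, improving within 24 to 72 hours: neither calls for tocilizumab. No conflict.
- Grade 3 or 4 ICANS without CRS, not improving within 24 to 72 hours: the narrative excludes tocilizumab and the table says to consider it. Conflict.

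The third case is a possible one, because the section itself says ICANS can occur independently of CRS. The conflict is confined to that case, apart from ICANS arising after CRS has resolved, where the narrative does not say whether the CRS context still applies.

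**2. Grade 4 ICANS: what each cohort's table says**

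- B1, B2, B3 (Substudy 02, 3 × 40 = about 120 planned): stop SAR444245. Pembrolizumab is not mentioned, and section 6.5.1 allows it to continue.
- C (Substudy 03, about 40): the same. Running total 120 + 40 = about 160.
- D1 (Substudy 04, about 40): stop both SAR444245 and pembrolizumab.
- D2 (Substudy 04, about 40): the same sentence applies, but these participants receive cetuximab and no pembrolizumab. Cetuximab is not mentioned, and section 6.5.1 allows it to continue.

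So about 160 planned participants are under one wording, about 40 under another, and about 40 under a sentence naming a drug they do not receive. The total is 160 + 40 + 40 = about 240.

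**3. Which table governs ICANS**

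The irAE tables (Table 6 in Substudies 02 and 03, Table 9 in Substudy 04) require permanent discontinuation of full study treatment for Grade 3 or 4 neurological toxicities. The ICANS tables allow SAR444245 to be restarted or stopped after Grade 3 ICANS. The irAE tables grade by CTCAE and the ICANS tables by ASTCT criteria. Nothing in the part shown says that ICANS falls under the neurological row, or that it does not. This is an unanswered question of precedence, not a demonstrated contradiction.

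**The case against.** The strongest reply is that the table's tocilizumab sentence presupposes CRS. It follows the sentence on concomitant CRS, refers back to CRS at its end, and closely resembles the persistent-CRS step in Substudy 04's Table 8. A dropped qualifier is a plausible explanation. But the block is headed as ICANS, the reference back to CRS concerns how steroids are repeated, and concomitant CRS has already been routed elsewhere. In Substudy 04 the block would be redundant if it covered only CRS.

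A second reply is that the section labels its management as recommendations to be weighed with site specialists, that the table says only to consider tocilizumab, and that section 6.5.3 leaves corrective therapy to the investigator's judgment. This stands as a limit on severity. It does not tell the investigator which of two recommendations the protocol makes.

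A third reply is that the Table 7 column is headed as SAR444245 guidance, so its silence on pembrolizumab is not an instruction to continue it, and a difference between substudies is not a contradiction within one. That is fair. Substudies 02 and 03 are silent on pembrolizumab, and section 6.5.1 permits continuation without requiring it. An unexplained difference remains, as does the misfit with D2.

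The rule in sections 6.5.1 and 6.5.4.4 to follow the most conservative recommendation does not settle the matter: it is worded for participants with several toxicities, not for one event described in two ways.

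Three stronger readings are tempting and not supported:

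- **Pooled data.** A reader might infer that pooled discontinuation or exposure data become non-comparable. The only pooling stated here is of efficacy in B1 and B2 (Substudy 02, section 9.4.1), which share one rule. The master protocol is not shown.
- **Frequency.** A reader might want a probability that the problem arises. No ICANS rate is given, and a chance of any Grade 3 or 4 ICANS at an assumed rate would not measure the narrower situations in which the texts diverge.
- **The irAE neurological row.** A reader might infer that it overrides the ICANS table. The grading scales differ and the row is not stated to cover ICANS.

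**Conclusion.** The point holds as an internal inconsistency in ICANS management. The tocilizumab narrative and table conflict in all three substudies, in one identifiable situation: Grade 3 or 4 ICANS without CRS that has not improved within 24 to 72 hours. The Grade 4 discontinuation wording differs between Substudies 02 and 03 on one side and Substudy 04 on the other, and in Substudy 04 it does not fit Cohort D2.

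The potential reach is all six cohorts for tocilizumab (about 240 planned participants); the Grade 4 wording difference also touches every cohort, as set out above. The number of events affected cannot be derived from the document. No effect on the sample size or the response-rate analysis is shown. The conclusion rests on the text of the three substudies as shown and assumes that the master protocol, which is not shown, contains no rule of precedence that resolves it. It takes no view on which clinical instruction is right.

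**What to change.** - In each of Substudies 02, 03 and 04, reconcile the section 6.5.4.5 narrative with its table so that both make the same statement on tocilizumab for Grade 3 and 4 ICANS with and without CRS.
- Reconcile the Grade 4 ICANS discontinuation wording across the three substudies, or give the reason for a deliberate difference. State explicitly what applies to each combination partner, including cetuximab in Cohort D2.
- State in each substudy whether the ICANS table or the neurological-toxicity row of the irAE table governs ICANS.

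The sponsor's safety team decides which instruction stands in each case. The cost is a text correction in three substudy documents at their next amendment, with no change to sample size, data collection or analysis.

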6.1.2 Non-investigational medicinal products

Please refer to the master protocol.

In case of permanent SAR444245 discontinuation and continuation of pembrolizumab treatment as part of AE management, SAR444245 premedication no longer needs to be administered.

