6.5 DOSE MODIFICATION

6.5.1 General rules

Dose modifications for SAR444245 are permitted according to the guidelines described in this section. Pembrolizumab dose reductions are not permitted. Pembrolizumab treatment may be interrupted or discontinued due to toxicity.

Dose modifications different from those stated in the protocol should only be made in consultation with the Sponsor, unless required for immediate participant safety.

Cycle delay (ie, Day 1 should be delayed for all IMPs) is permitted in case of treatment-emergent adverse event (TEAE). Dose modification will be made according to the worst grade of toxicity observed within a cycle. If a participant experiences several toxicities and there are conflicting recommendations, the most conservative recommended dose adjustment should be followed.

In participants who have SAR444245 dose reduction due to SAR444245 related Grade ≥ 3 treatment-related adverse events (TRAEs), SAR444245 dose may be re-escalated to █ $\mu\text{g}/\text{kg}$ if:

- no SAR444245 related Grade ≥ 3 TRAE or clinically significant laboratory abnormality within at least 2 subsequent cycles, AND
- both Investigator and Sponsor agree that the participant has clinical benefit.

Administration of the study treatment will be discontinued in the event of a TEAE that persists despite appropriate dose modifications or any other TEAE that, in the opinion of the Investigator, warrants discontinuation.

If any of the IMP components is permanently discontinued, the other IMP component can be continued until disease progression or other criteria as detailed in Section 7.1.1 of the master protocol are met. In this case, it is partial permanent discontinuation, and the end of treatment (EOT) assessment will be 30 days after the date of the last administration of the remaining IMP. When all IMP components are permanently discontinued, it is full permanent discontinuation.

All changes to study treatment administration must be recorded in the electronic case report form (e-CRF).

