6.5.4.4 Immune-related adverse events

AEs associated with pembrolizumab exposure may represent an immunologic etiology. These immune-related AEs (irAEs) may occur shortly after the first dose or several months after the last dose of pembrolizumab treatment and may affect more than one body system simultaneously. IrAEs are thought to be caused by unrestrained cellular immune responses directed at the normal host tissues. Therefore, early recognition and initiation of treatment is critical to reduce complications. Based on existing pembrolizumab clinical study data, most irAEs were reversible and could be managed with interruptions of pembrolizumab, administration of corticosteroids and/or other supportive care.

Investigators must be extremely vigilant and be ready to intervene early in the management of irAEs because the onset of symptoms of irAEs (eg, pneumonitis) may be subtle. For suspected irAEs, adequate evaluation should be performed to confirm etiology or exclude neoplastic, infectious, metabolic, toxin, or other etiologic causes. Additional procedures or tests such as bronchoscopy, endoscopy, skin biopsy may be included as part of the evaluation. Based on the severity of irAEs, withhold or permanently discontinue pembrolizumab and/or SAR444245 and administer corticosteroids.

SAR444245 may increase the incidence and severity of these events.

Dose modification and toxicity management guidelines for irAEs are provided in [Table 6](#). Of note, when study interventions are administered in combination, if the AE is considered immune-related, both drugs in the combination should be held according to recommended dose modifications. If a participant experiences several irAEs, the most conservative recommendation should be followed.

The CTCAE V5.0 must be used to grade the severity of AEs.

When pembrolizumab can be restarted, it should be administered at the initial planned dose and schedule as no modification is allowed:

- If the toxicity does not resolve or the criteria for resuming treatment are not met, the participant must be discontinued from all study drugs.

If the toxicities do resolve and conditions are aligned with what is defined in [Table 6](#), the combination of SAR444245 and pembrolizumab may be restarted at the discretion of the investigator. In these cases where the toxicity is attributed to the combination or to SAR444245 alone, re-initiation of pembrolizumab as a monotherapy may be considered after communication with the Sponsor.

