irAEs	Toxicity grade (CTCAE V5.0)	Action with pembrolizumab and SAR444245	Corticosteroid and/or other therapies	Monitoring and follow-up
a	SAR444245 to be withheld plus pembrolizumab to be withheld corresponds to "cycle delay".			
b	Permanently discontinuation of full study treatment.			
c	AST/ALT: >3.0 - 5.0 x ULN if baseline normal; >3.0 - 5.0 x baseline, if baseline abnormal; bilirubin: >1.5 - 3.0 x ULN if baseline normal; >1.5 - 3.0 x baseline if baseline abnormal.			
d	AST/ALT: >5.0 to 20.0 x ULN, if baseline normal; >5.0 - 20.0 x baseline, if baseline abnormal; bilirubin: >3.0 - 10.0 x ULN if baseline normal; >3.0 - 10.0 x baseline if baseline abnormal.			
e	AST/ALT: >20.0 x ULN, if baseline normal; >20.0 x baseline, if baseline abnormal; bilirubin: >10.0 x ULN if baseline normal; >10.0 x baseline if baseline abnormal.			
f	The decision to withhold or permanently discontinue pembrolizumab and SAR444245 is at the discretion of the investigator or treating physician. If control achieved or ≤Grade 2, pembrolizumab and SAR444245 may be resumed.			
g	Events that require discontinuation include but are not limited to: encephalitis and other clinically important irAEs (eg. vasculitis and sclerosing cholangitis).			
	AE(s)=adverse event(s); ALT= alanine aminotransferase; AST=aspartate aminotransferase; CTCAE=Common Terminology Criteria for Adverse Events; DRESS=Drug Rash with Eosinophilia and Systemic Symptom; GI=gastrointestinal; ir=immune related; IV=intravenous; SJS=Stevens-Johnson Syndrome; T1DM=type 1 diabetes mellitus; TEN=Toxic Epidermal Necrolysis; ULN=upper limit of normal.			
	Note: Non-irAE will be managed as appropriate, following clinical practice recommendations.			

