6.5.4.5 Immune Cell-Associated Neurotoxicity Syndrome (ICANS)

Immune cell-associated neurotoxicity syndrome (ICANS) is a neuropsychiatric syndrome which is frequently associated with CRS; however, it is specifically excluded from the definition of CRS and can occur during the course of CRS, after its resolution, or independently from CRS. Clinical findings can be progressive and may include aphasia, altered level of consciousness, impairment of cognitive skills, motor weakness, seizure, and cerebral edema. Severity is evaluated using the ASTCT Consensus grading scale, with ICE score for encephalopathy assessment (Section 10.11 of the master protocol). Recommendations for ICANS management mainly include the use of steroids, whereas tocilizumab should only be used in the context of CRS, as outlined in [Table 10](#). The proposed management should be considered only as recommendations and in light of recommendations from site specialist.

Table 10 - Guidelines for the management of immune Cell-Associated Neurotoxicity Syndrome (ICANS)

Event severity (ASTCT Consensus Grading criteria)	Recommended SAR444245 dose modification and supportive care guidelines
Mild Grade 1 ICE score 7-9. Awakens spontaneously	No intervention required other than close clinical monitoring.
Moderate Grade 2 ICE score 3-6. Awakens to voice.	SAR444245^a should be delayed. Treatment with IV corticosteroids should be initiated as needed. SAR444245 may be resumed only after participant recovery or improvement to Grade 1 after corticosteroid taper. Consideration for reduction of SAR444245 dose to █ µg/kg as per Investigator with Sponsor consultation.
Severe or Life-threatening Grade 3 ICE score 0-2. Awakens only to tactile stimulus. Any clinical seizure focal or generalized that resolves rapidly or nonconvulsive seizures on EEG that resolve with intervention.	If Grade 3 ICANS, SAR444245 should be delayed. When symptoms have resolved or improved to Grade 1 after corticosteroid taper, SAR444245 can be either restarted at █ µg/kg or permanently discontinued, as clinically indicated, and upon discussions between the Investigator and Sponsor.

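### The Grade 4 ICANS recommendation stops only SAR444245 in substudies 02 and 03 but stops pembrolizumab as well in substudy 04, for the same regimen and with no reason in the text shown

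*Protocol*

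**What the plan says.** Section 6.5.4.5 of each substudy has a table for managing ICANS by grade. For Grade 4, Table 7 in substudies 02 (Cohorts B1 to B3) and 03 (Cohort C) reads "If Grade 4 ICANS, SAR444245 should be permanently discontinued". It does not mention pembrolizumab. Table 10 in substudy 04, which includes Cohort D1, reads "If Grade 4 ICANS, both SAR444245 and pembrolizumab should be permanently discontinued".

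The section describes the status of this guidance: "The proposed management should be considered only as recommendations and in light of recommendations from site specialist".

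Two other rules bear on pembrolizumab in substudies 02 and 03.

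- **Section 6.5.1** deals with permanent discontinuation of one IMP component and states that "the other IMP component can be continued until disease progression or other criteria as detailed in Section 7.1.1 of the master protocol are met". Section 6.1.2 foresees that path and drops the SAR444245 premedication "In case of permanent SAR444245 discontinuation and continuation of pembrolizumab treatment as part of AE management".
- **Section 6.5.4.4** says that "if the AE is considered immune-related, both drugs in the combination should be held according to recommended dose modifications". In its Table 6, Grade 3 or 4 neurological toxicity leads to permanent discontinuation, which a footnote defines as "Permanently discontinuation of full study treatment".

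**The concern.** Sites giving the same two drugs at the same doses start from different advice after the same life-threatening event. In these tables Grade 4 ICANS includes coma, a life-threatening seizure lasting more than 5 minutes, and diffuse cerebral edema. A Cohort D1 site is advised to stop both drugs. A site in Cohorts B1 to B3 or C is advised to stop SAR444245, and Section 6.5.1 then leaves pembrolizumab open.

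Within substudies 02 and 03 there is a second difference. The same clinical picture can be handled as ICANS under Table 7 or as an immune-related neurological toxicity under Table 6. Only the second route ends pembrolizumab. What is at stake is consistent handling of pembrolizumab after a severe neurological event, not any trial estimate.

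**Working it through.** No plan figure needs to be reproduced. The check compares the texts and makes one count.

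**1. Is the regimen the same?** The IMP overview tables in Section 6.1.1 of all three substudies list SAR444245 24 µg/kg Q3W and pembrolizumab 200 mg Q3W. Cohort D1 is the substudy 04 cohort that receives this pair. So yes.

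**2. Grade 4 ICANS side by side.**

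| Substudy | Cohorts on pembrolizumab | Table | Drug(s) permanently stopped |
|---|---|---|---|
| 02 | B1, B2, B3 | 7 | SAR444245 |
| 03 | C | 7 | SAR444245 |
| 04 | D1 | 10 | SAR444245 and pembrolizumab |

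All three action columns are headed as SAR444245 dose guidance. The heading therefore cannot explain why one names pembrolizumab and the others do not.

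**3. Does another rule in substudies 02 and 03 close the gap?**

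- Section 6.5.3 requires an IMP delay for Grade 3 or higher treatment-related events, but only for those not covered in Tables 3 to 8. ICANS is Table 7, so this rule does not reach it.
- Section 6.5.1 tells sites to follow the most conservative adjustment when several toxicities give conflicting advice. It does not say what to do when one event fits two tables.
- Table 6 ends all study treatment at neurological Grade 3 or 4, but only if the event is handled as immune-related. The ICANS section does not refer to that row.

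Under Table 7 with Section 6.5.1, pembrolizumab may continue. Under Table 6 it may not.

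**4. Is a reason given?** The visible amendment entries for the three substudies do not mention ICANS, and the introductions to the ICANS sections are nearly identical. No reason appears in the text shown.

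**5. How many planned participants come under each wording?** Section 9.2 of each substudy plans about 40 per cohort.

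- SAR444245 only: 3 × 40 (B1 to B3) + 40 (C) = 160
- Both drugs: 40 (D1)
- Shares: 160 / (160 + 40) = 80%, and 40 / 200 = 20%

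Cohort D2 is left out because it receives cetuximab, not pembrolizumab. The shares cover only the cohorts in the part of the document shown.

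**The case against.** The strongest reply is that substudy 04 is the odd one out. Its table also serves Cohort D2, yet it names pembrolizumab and not cetuximab. Neighbouring guidance follows the SAR444245-only pattern: Grade 3 or 4 vascular leak syndrome in all three substudies, and Grade 4 cytokine release syndrome in substudies 03 and 04, stop SAR444245 without stopping pembrolizumab. On this view the sponsor could equally align substudy 04 with the others, and nothing in the documents shows that pembrolizumab alone is unsafe after recovery. This stands in part: the documents do not prove which direction is clinically right. But stopping both is more than a preference. It is what Table 10 says for the identical regimen, and it is what the Grade 4 neurological row of Table 6 says in substudies 02 and 03 themselves.

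The guidance is also non-binding. The investigator makes the final decision, may end treatment for any event judged to warrant it, and is told to involve a neurologist where indicated. That stands and limits the weight of the point. It explains how a site may depart from a recommendation, not why sites start from different ones.

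A reader might infer that substudies 02 and 03 tell sites to continue pembrolizumab after coma or cerebral edema. They do not. Table 7 is silent, and Section 6.5.1 permits continuation without requiring it, subject to master-protocol criteria that are not shown. A reader might also infer that the sponsor has no rationale at all. That cannot be established, because the master protocol and the first part of the document are not available.

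**Conclusion.** The discrepancy is real and minor. In the text shown, the Grade 4 ICANS recommendation stops only SAR444245 in substudies 02 and 03 and stops both drugs in substudy 04, for the same regimen. In substudies 02 and 03 it also departs from the Grade 4 neurological row of Table 6, so the handling of pembrolizumab turns on the label the site gives the event.

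The 160 of 200 planned participants should not be read as people harmed or expected to have the event. It is only the number enrolled under that row if each cohort reaches 40. The protocol gives no ICANS rate, so no event count or amount of harm can be estimated.

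The conclusion assumes that nothing in the master protocol, including its Section 7.1.1, already stops pembrolizumab after Grade 4 ICANS or explains the difference.

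**What to change.** In the Grade 4 row of Table 7 in substudies 02 and 03, replace the sentence with the one from substudy 04: "If Grade 4 ICANS, both SAR444245 and pembrolizumab should be permanently discontinued". This aligns Grade 4 across the three substudies and with the Grade 4 neurological row of Table 6.

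The cost is one sentence in each of two tables and no new procedure. A participant in Cohorts B1 to B3 or C with Grade 4 ICANS would lose the discretionary option of pembrolizumab alone, which Section 6.1.2 foresees. If the sponsor means to keep that option, a sentence giving the reason, and saying which table governs when an event fits both, would also settle the point.

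The change does not touch Grade 3. In all three substudies the ICANS table says "If Grade 3 ICANS, SAR444245 should be delayed" and allows a restart after recovery, while the immune-related table ends all study treatment for a Grade 3 neurological toxicity.
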